This study was registered with ClinicalTrials.gov as NCT01901419 after obtaining approval of Tri-Service General Hospital Institutional Review Board (TSGHIRB-1-102-05-049). Patients receiving elective cardiac surgery with cardiopulmonary bypass were recruited and signed the written informed consent. Those with complicated comorbidities were excluded, such as chronic hepatic or renal insufficiency, or acute cardiopulmonary failure requiring mechanical ventilation, intra-aortic balloon pump, or extracorporeal membrane oxygenation. Patients were randomly assigned to receive either NTG infusion 1-5 mcg/kg/min (NTG group), the dose labelled to maintain intraoperative hypotension, or 0-0.1 mcg/kg/min (control group), the dose labelled for acute cardiac insufficiency, during rewarming of hypothermic CPB. Those undergoing normothermic CPB decided by the surgeon intraoperatively were not analyzed.

Anesthesia and cardiopulmonary bypass

Routine physiologic monitoring, including three-lead electrocardiogram, pulse oximetry and an invasive arterial blood pressure monitoring were set up immediately before anesthesia induction. In addition, cardiac output was continuously monitored (FloTrac; Edwards Lifesciences, Irvine, CA, USA). Cerebral oximetry (Fore-Sight oximeter; CASMED, Branford, CT, USA), based on near-infrared spectroscopy technology, was applied on the forehead until the end of surgery.

All patients received general anesthesia with midazolam 5 mg, fentanyl 1.5-3.0 mcg/kg, propofol 0.5-1.5 mg/kg, and cisatracurium 0.1-0.2 mg/kg for induction, as well as sevoflurane or isoflurane for maintenance after tracheal intubation. A pulmonary artery catheter (Swan-Ganz Thermodilution catheter 7.5 Fr; Edwards Lifesciences, CA, USA) was placed through right internal jugular vein for postoperative monitoring. Transesophageal echocardiography

2016-0504-v2 - 2 -

was used to monitor real-time cardiac performance throughout the whole procedure. Minute ventilation was adjusted to maintain end-tidal CO₂ 40 ± 5 mmHg, confirmed by serial arterial blood gas analyses. After achieving anticoagulation (activated clotting time >350 seconds) by intravenous administered heparin 300 U/kg prior to cannulation, standard hypothermic CPB (Sarns 8000, Terumo, Ann Arbor, MI) with an extracorporeal membrane oxygenator (Capiox®SX 18, Terumo, Ann Arbor, MI) were carried out in sequence to maintain the body temperature at 26-30 °C during surgery. The perfusionist adjusted the pump flow to obtain an adequate output of 2.2 l/m² of body surface area and adjusted sevoflurane concentration on the vaporizer, to keep mean arterial blood pressure 50-80 mmHg.

Treatment protocol

Before rewarming, the patients were randomly assigned to NTG group with NTG infusion 1-5 mcg/kg/min or control group with 0-0.1 mcg/kg/min. The infusion rate would be tapered if there was profound hypotension (mean arterial pressure <40 mmHg) or cerebral desaturation (absolute saturation value <60 or relative drop to <80% of baseline value each side). Following standard rewarming and deaerating, the pump flow was reduced to 0.5 l/min for release of aortic clamp and was weaned with routine inotropic support, including dopamine 3-8 mcg/kg/min and additional dobutamine, epinephrine, or norepinephrine infusion for acceptable cardiac output. Further intra-aortic balloon pump or extracorporeal membrane oxygenation would be applied for cardiopulmonary support, if needed. Heparin effect was neutralized with protamine sulfate after stop of bypass. All patients were transferred to the cardiovascular surgical intensive care unit (ICU) with endotracheal intubation after the operations were finished. According to the routine criteria, extubation was performed after obtaining oriented consciousness, normothermia (patient rewarmed and shivering controlled), and hemodynamic stability with no uncontrolled arrhythmias and no excessive bleeding (as defined by loss of < 100 ml/h).

2016-0504-v2 - 3 -

Data collection

Arterial blood gas analysis was routinely examined perioperatively, including before incision, after heparin administration, before aortic unclamping, after aortic unclamping, after protamine administration, and immediately upon ICU admission by GEM Premier 3000 (Instrumentation Laboratory, Lexington, MA, USA), including plasma lactate (detectable limit, 0.3 to 20 mmol/L) and glucose (detectable limit, 20-500 mg/dL) levels. The activated clotting (or coagulation) time was tested by ACT Plus (Medtronic, Minneapolis, MN, USA) after heparin administration, during CPB, after protamine administration, and before the end of surgery (if needed). The perioperative variables were collected, including acid-base status, glucose level, and urine output. Postoperative inotropic use, time to extubation, lengths of ICU and hospital stay, and 30-day mortality were also recorded from the hospital's registry database.

Statistical analysis

All values were expressed as mean \pm SD or number unless otherwise stated. The Student t-test was applied to compare means of continuous variables. Pearson's Chi-square test or Fisher's exact test was used for categorical variables. All statistical tests were two-tailed, with the level of significance set at P values <0.05. Data analysis was performed using the SPSS for Windows.

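### Does leaving normothermic bypass cases out of the analysis amount to a discretionary exclusion after randomisation?

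*Combined protocol and SAP*

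**What the plan says.** The opening paragraph, which covers recruitment and assignment, sets entry broadly: "Patients receiving elective cardiac surgery with cardiopulmonary bypass were recruited and signed the written informed consent". It lists comorbidity exclusions, states that patients were randomised to a higher or lower nitroglycerin infusion "during rewarming of hypothermic CPB", and ends with the rule at issue: "Those undergoing normothermic CPB decided by the surgeon intraoperatively were not analyzed".

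The section Anesthesia and cardiopulmonary bypass describes hypothermic bypass as the standard procedure. Anticoagulation, cannulation and cooled bypass "were carried out in sequence to maintain the body temperature" at 26-30 °C.

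The Treatment protocol section follows and opens with the only statement on the timing of allocation: "Before rewarming, the patients were randomly assigned to NTG group". Rewarming, deaeration and release of the aortic clamp come next.

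The Statistical analysis section names tests ("The Student t-test was applied to compare means of continuous variables", with chi-square or Fisher's exact test for categorical variables). It does not name an analysis population. The documents do not mention allocation concealment or blinding of the surgeon, and they give no sample size and no count of normothermic cases.

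**The concern.** Three features of the wording invite suspicion. Hypothermia is not among the entry criteria. The rule follows the sentence on random assignment and speaks of analysis, whereas the comorbidity criteria are worded as exclusions. And a statement that assignment came before rewarming, read literally, gives a latest time but no earliest one.

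If allocation had been opened at consent or at induction, the rule would remove randomised patients on a clinician's decision with no stated criteria. If the surgeon also knew or could guess the arm, the two analysed groups might differ in prognosis for reasons other than treatment. With no planned report of exclusions by arm, a reader could not detect this.

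**Working it through.** **Order of events.** The plan has no figure to reproduce, so the first check sets the statements side by side.

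1. Cooled bypass is described first, then assignment before rewarming, then the infusion, then rewarming and unclamping. The account runs in procedural order.
2. The Data collection section uses before and after labels in the same way to mark blood-gas sampling points. The label for sampling before clamp release names a point in the operation and does not mean any earlier time. Read alike, the timing of assignment also marks a step.
3. The assigned treatment exists only while a cooled patient is rewarmed. Whether the patient is cooled is settled before there is anything to rewarm. A normothermic patient has no such phase and cannot be among patients assigned just before it.
4. Consent came before surgery and the temperature decision was made during it. Some patients would therefore consent, be found normothermic in theatre, and never reach assignment. The phrase that they were not analysed describes them without strain.

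On this reading every randomised patient is hypothermic, nobody is removed after randomisation, and the bias is zero.

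**If allocation came earlier.** All inputs below are assumed: 50 or 100 patients randomised per arm, fractions p1 and p0 excluded, and excluded patients better by d standard deviations (SD).

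- Bias in the difference = (p1 − p0) × d.
- Analysed numbers: n1 = n(1 − p1), n0 = n(1 − p0).
- Shift of the test statistic = bias / √(1/n1 + 1/n0).
- Type I error = P(|Z + shift| > 1.96).

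*Exclusion unrelated to arm, 10% in each.* Bias = 0 and type I error = 0.050. The standard error is multiplied by √(1/0.9) = 1.054, a rise of 5.4%.

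*Exclusion differing by arm.*

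| Assumed exclusion | d | n per arm | Bias (SD) | Shift | Type I error |
|---|---|---|---|---|---|
| 10% vs 5% | 0.5 | 50 | 0.025 | 0.12 | 0.052 |
| 10% vs 5% | 1 | 50 | 0.05 | 0.05/√(1/45 + 1/47.5) = 0.24 | 0.057 |
| 20% vs 5% | 1 | 100 | 0.15 | 0.15/√(1/80 + 1/95) = 0.99 | 0.167 |

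The result depends on the inputs chosen, and the documents supply none of them.

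**Keeping normothermic patients in the primary analysis.** These patients receive no rewarming infusion, so keeping them dilutes the effect. For an assumed true effect of 0.5 SD and a fraction p normothermic in each arm, with no prognostic difference, the shift is 0.5(1 − p)√(n/2) if they are kept and 0.5√(n(1 − p)/2) if they are left out.

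- p = 10%, n = 50: 2.25 against 2.37, power 0.61 against 0.66.
- p = 10%, n = 100: 3.18 against 3.35, power 0.89 against 0.92.

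**The case for a change.** The strongest case for a change is that the order of paragraphs does not say when an allocation was opened. An assignment drawn before surgery would also have been made before rewarming. The authors write of exclusion for comorbidities and of not analysing for this rule, which may reflect a real difference. They also say immediately before when timing the set-up of monitoring, so they could have been equally exact here. With no statement on concealment, blinding or the analysis set, the documents do not rule out early allocation, and one sentence would settle it.

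The point about wording stands: the time of allocation relative to the temperature decision is not stated outright. The step from there to bias does not. Early allocation alone is not enough, because the infusion starts later and cannot cause the temperature decision. The surgeon must also know or guess the arm, let it influence the choice of temperature, and do so for patients whose prognosis differs. Silence leaves each of these possible but is evidence for none.

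**Conclusion.** This is a gap in description that the rest of the text fills sensibly. The natural reading is that assignment followed established hypothermia. Normothermic patients were then never randomised, and the rule acts as an eligibility condition with zero effect on the comparison. Tying allocation to rewarming would repeat what the plan most naturally already does, so it would change no result.

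The alternative of analysing normothermic patients in their assigned arm matters only if some were allocated early. It would then put patients who cannot receive the infusion into the primary comparison, at a cost of about 3 to 5 points of power under the assumptions above. Reasonable statisticians differ on that trade-off.

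The conclusion rests on reading the sections in procedural order and on the fact that the treatment is defined only for rewarming after hypothermia. It would need another look if records showed patients allocated before the temperature decision and normothermic exclusions that differed by arm. Nothing in the documents suggests either.

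### Do the 50-80 mmHg bypass pressure target and the below-40 mmHg taper trigger conflict, and does sevoflurane titration undermine the comparison of arms?

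*Combined protocol and SAP*

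**What the plan says.** The Anesthesia and cardiopulmonary bypass section sets two targets on bypass. For flow: "The perfusionist adjusted the pump flow to obtain an adequate output of 2.2 l/m² of body surface area". For pressure, the perfusionist "adjusted sevoflurane concentration on the vaporizer, to keep mean arterial blood pressure 50-80 mmHg". No phase of bypass and neither arm is exempted.

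The opening section on patients and randomisation places the study infusion "during rewarming of hypothermic CPB", so both rules apply at the same time. It describes the active arm as "NTG infusion 1-5 mcg/kg/min (NTG group), the dose labelled to maintain intraoperative hypotension"; control patients receive 0-0.1 mcg/kg/min.

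The Treatment protocol section gives the taper rule: "The infusion rate would be tapered if there was profound hypotension (mean arterial pressure <40 mmHg", followed by an alternative trigger, "cerebral desaturation (absolute saturation value <60 or relative drop to <80% of baseline value each side". Either one is enough.

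The Data collection section states: "The perioperative variables were collected, including acid-base status, glucose level, and urine output". It also names blood gases with lactate and glucose, clotting times, and later outcomes ("Postoperative inotropic use, time to extubation, lengths of ICU and hospital stay, and 30-day mortality were also recorded"). Vaporizer concentration, mean pressure, pump flow and the NTG rate actually given are not named.

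**The concern.** Read on their pressure figures alone, the two sections seem to pull apart. At 45 mmHg, say, one treats the pressure as out of range, while the other's pressure clause leaves the infusion alone. The active dose is described as a hypotensive one, so such pressures are foreseeable mainly in that arm, and an unclear instruction there would be a safety matter.

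There is also a statistical worry. If the pressure target is kept, NTG patients may receive less sevoflurane. If it is not kept, they may spend longer at low perfusion pressure. A difference in lactate could then reflect NTG itself, the volatile anaesthetic or the pressure, and the data named as collected would not show which. If this biased the comparison of arms, the trial's main result would be in doubt.

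**Working it through.** The documents give no sample size, power or event figure bearing on this point, so there is no planned figure to reproduce. The check sets the rules side by side and then asks what the comparison of arms estimates.

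**Step 1: width of the band.** Lower limit of the target (Anesthesia and cardiopulmonary bypass) = 50 mmHg. Pressure trigger for taper (Treatment protocol) = below 40 mmHg. Width = 50 − 40 = 10 mmHg.

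**Step 2: can both rules be followed at every pressure?** A contradiction needs a state in which obeying one rule breaks the other.

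| Mean pressure | Target rule | Taper rule, no desaturation | Taper rule, desaturation | Both can be followed? |
|---|---|---|---|---|
| Above 80 mmHg | Adjust sevoflurane | No taper required | Taper | Yes |
| 50-80 mmHg | In range | No taper required | Taper | Yes |
| 40 to below 50 mmHg | Adjust sevoflurane | No taper required | Taper | Yes |
| Below 40 mmHg | Adjust sevoflurane | Taper | Taper | Yes |

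No row forces a breach. The rules act on different drugs: one is a target, the other a safety limit beneath it. What the text leaves open is one cell, 40 to below 50 mmHg without desaturation. There a taper is not required, but it is not forbidden either, since the active dose is a range (1 to 5 mcg/kg/min, a factor of 5/1 = 5) and the taper sentence says only when the rate must come down.

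**Step 3: is the band unguarded?** No. The desaturation trigger carries no pressure condition, and the Anesthesia and cardiopulmonary bypass section keeps cerebral oximetry running to the end of surgery.

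**Step 4: what the comparison of arms estimates.** Suppose assignment affects lactate directly, through sevoflurane and through pressure:

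total effect = direct effect + effect through sevoflurane + effect through pressure (treating the three as additive, for illustration).

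Randomisation identifies the left-hand side. Sevoflurane changes come after assignment and, on this argument, because of it, so they form part of the strategy being compared. They are not a baseline imbalance. The planned t-tests and chi-square or Fisher tests estimate and test that total difference without needing the terms on the right.

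**Step 5: would more fields separate the terms?** Tabulating vaporizer setting, pump flow, NTG rate and time below 50 mmHg by arm would describe the pathways. It would not divide the effect among them, because those quantities were not randomised, and patients whose pressure falls may differ in ways that also affect lactate. Adjusting the main comparison for them could introduce bias.

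**Step 6: what absence from the list shows.** The perioperative list opens with the word *including*, so it is not exhaustive. Invasive arterial pressure and cerebral oximetry are described as monitored. The documents do not show that these values went unrecorded.

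**The case for a change.** The strongest case for a change runs as follows. No sentence ranks the target against the triggers. Pressures below 50 mmHg are to be expected mainly in one arm. During rewarming the text names sevoflurane as the means of pressure control and, arguably, pump flow, which has its own target; vasoactive drugs appear only for weaning. Two teams could follow this text and manage the same patient differently. Following both rules together produces exactly the difference in sevoflurane exposure that is feared. Writing down the interaction and copying a few fields from monitoring and perfusion records would cost little.

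Part of this stands. The interaction is unspecified at 40-49 mmHg without desaturation, and desaturation is a different signal that does not settle that case. Sevoflurane concentration, mean pressure and actual NTG rate are not named as collected. A by-arm description of them would help a reader who wants to understand mechanism.

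The stronger claims do not stand. There is no contradiction, so no instruction has to be withdrawn. Variation in management inside the band is part of how each strategy was delivered, and it does not bias the comparison between strategies. That the arms differed in sevoflurane is conjecture, since no data are given. A request to word the conclusion as a strategy effect has no target: the documents contain no conclusion, and the text available names no primary endpoint, so lactate as the result at stake is itself an assumption.

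**Conclusion.** The concern does not call for a change. The two thresholds are read correctly and the band between them is 10 mmHg wide, but a sevoflurane-held target and a lower safety trigger for the study drug form a workable tiered scheme, with desaturation as an added trigger at any pressure. What is missing is a sentence on how they work together at 40-49 mmHg without desaturation. Any such sentence is a clinical matter for the investigators, and no view is taken here on either threshold.

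For the statistics, following the plan as written still gives a sound comparison of two infusion strategies under pressure-titrated sevoflurane. The significance level and the choice of test are untouched. The limit is on interpretation: an observed difference belongs to the strategy and cannot be credited to NTG's direct action alone. Analysts can respect that in reporting, and can describe vaporizer settings, pressure and infusion rate by arm if they were recorded.

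This rests on three assumptions: patients are compared as randomised; the question is the effect of the assigned strategy; and the same target and taper rules apply in both arms, as the text implies by exempting neither. The number of patients entering the band, and any resulting difference in sevoflurane or lactate, cannot be derived from the documents.

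### Is postoperative inotropic use uninformative because dopamine is routine at weaning and mechanical support is not a listed data item?

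*Combined protocol and SAP*

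**What the plan says.** Three parts of the combined protocol and SAP bear on this.

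- **Treatment protocol.** After rewarming and deairing, bypass "was weaned with routine inotropic support, including dopamine 3-8 mcg/kg/min and additional dobutamine, epinephrine, or norepinephrine infusion for acceptable cardiac output". The next sentence adds: "Further intra-aortic balloon pump or extracorporeal membrane oxygenation would be applied for cardiopulmonary support, if needed". Together they describe a ladder: a routine first step, additional drugs according to cardiac output, then mechanical support.
- **Data collection.** "Postoperative inotropic use, time to extubation, lengths of ICU and hospital stay, and 30-day mortality were also recorded from the hospital's registry database". Nothing more is said about the inotrope variable. The sentence before it gives perioperative variables as an open list of examples. Neither sentence mentions a balloon pump or ECMO.
- **Statistical analysis.** "The Student t-test was applied to compare means of continuous variables". For categorical data, "Pearson's Chi-square test or Fisher's exact test was used for categorical variables". Every comparison is two-sided at the 0.05 level. No variable is assigned to a test, and no primary or secondary outcome is named.

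The document gives no sample size, power or expected event rate.

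**The concern.** If inotropic support is routine at weaning, most or all patients in both arms will have had dopamine. A count of patients on any inotrope could then sit close to 100% in each arm and show no difference whatever nitroglycerin did. The informative steps are the later ones: a second drug, a balloon pump or ECMO. The listed data do not visibly separate a patient on routine dopamine from one on several agents plus mechanical support. Patients already needing mechanical support for acute cardiopulmonary failure are excluded at entry, so its use after weaning would generally be new and of interest.

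At stake would be a report of no difference in inotropic use despite a real difference in the need for escalated support, in a trial of a vasodilator given just before weaning.

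**Working it through.** **1. Nothing to reproduce.** The document states no rate, sample size or power. Every rate and arm size below is an assumption. The only input from the plan is the two-sided 0.05 level with chi-square or Fisher tests.

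**2. What pooling would do if the variable were yes/no.** Let e be the proportion in an arm who need additional agents, and f the fraction of the remaining patients still on dopamine when use is counted. Then

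any use = e + f(1 − e), and the difference between arms = (e₁ − e₂)(1 − f).

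Take e₁ = 0.40 and e₂ = 0.20. With f = 0.5, any use is 0.40 + 0.5 × 0.60 = 0.70 against 0.20 + 0.5 × 0.80 = 0.60. Chi-square power, by exact enumeration of two binomials:

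| Measure | Rates | 50 per arm | 100 per arm |
|---|---|---|---|
| Additional agents | 40% vs 20% | 60% | 88% |
| Any use, f = 0.5 | 70% vs 60% | 18% | 32% |
| Any use, f = 0.7 | 82% vs 76% | 12% | 18% |
| Any use, f = 0.9 | 94% vs 92% | 6% | 8% |
| Any use, f = 1 | 100% vs 100% | 0 | 0 |

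So the loss is real if the variable is yes/no and f is large. The document fixes neither.

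**3. A high rate alone is not the problem.** Setting 40% vs 20% by chi-square beside 98% vs 96% by Fisher (1% and 4% power at 50 and 100 per arm) or 95% vs 90% by Fisher (6% and 19%) changes both the gap and the test. With the gap held at 20 points, 95% vs 75% by Fisher has 75% and 98% power, more than 40% vs 20%. Away from the ceiling, a 5-point gap of 45% vs 40% by chi-square has only 9% and 12%. Power depends heavily on the size of the gap. What matters is how far pooling shrinks it, and that depends on the unknown f.

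**4. Is the variable yes/no, and is f near 1?** The Treatment protocol places dopamine at weaning, in the operating room. Data collection refers to postoperative use. No text says how many patients arrive in the ICU on an inotrope or how long they stay on one. Nor does any text say that use is coded as present or absent. Dose, number of agents and duration all fit the wording, and the Statistical analysis section supplies a t-test for continuous measures.

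**5. Are the sickest patients lost?** Mechanical support is written as a step beyond inotropes. A patient who reaches it would most likely count as an inotrope user, so the patient is not distinguished rather than missed. The same sentence in Data collection also records time to extubation, ICU and hospital stay, and 30-day mortality, in which severe cases can show.

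**6. Is mechanical support unrecorded?** It is unlisted. Balloon pump or ECMO at weaning is a perioperative event, and the perioperative list is open. A two-sentence data description does not establish that such an event was left out.

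**The case for a change.** The strongest reply is that the argument does not need a literal ceiling. The table shows a true 20-point difference halved to 10 points even when half the non-escalated patients are off dopamine, with power at 50 per arm falling from 60% to 18%. An undefined variable can also be coded after the data are seen. A definition based on support beyond routine dopamine would avoid both problems for a few chart fields, and the registry sentence, unlike the perioperative one, is written as a closed list.

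Most of the arithmetic stands: pooling routine with escalated use dilutes a difference, whatever the exact rate. It stands only for a yes/no coding, which the plan does not prescribe. The point about late choice of coding is fair, but it is a point about missing detail, and it applies to a variable the plan merely records beside several others. The suggested composite is one reasonable definition. Dose, number of agents or duration would also separate routine from escalated support.

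**Conclusion.** No change to the plan is called for. The accurate residue is that postoperative inotropic use has no stated agents, time window or scale, and that balloon pump and ECMO use are not among the listed data. No rule in the plan yields a wrong result: nothing requires a yes/no count, and the near-100% rate is inferred from treatment at a different time point. An analyst who knows that dopamine is routine at weaning would sensibly report additional agents, doses or duration, and would mention mechanical support where it occurred.

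The possible size runs from no loss (a graded measure, or escalation reported separately) to a complete loss of power (yes/no coding with every patient still on dopamine). For yes/no coding with half the non-escalated patients still on dopamine, power falls from 60% to 18% at 50 per arm and from 88% to 32% at 100 per arm. These figures rest on assumed escalation rates of 40% and 20% and on assumed arm sizes, so they illustrate the mechanism and do not measure a defect in this trial.

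### No listed blood gas is tied to allocation or to the start of the infusion, so lactate, glucose and acid-base balance at that point can be neither checked nor adjusted for

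*Combined protocol and SAP*

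**What the plan says.** Treatment protocol fixes allocation: "Before rewarming, the patients were randomly assigned to NTG group with NTG infusion 1-5 mcg/kg/min or control group with 0-0.1 mcg/kg/min". The opening paragraph on recruitment and randomisation places the infusion "during rewarming of hypothermic CPB".

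Data collection lists six blood-gas times: "before incision, after heparin administration, before aortic unclamping, after aortic unclamping, after protamine administration, and immediately upon ICU admission". The analyser output is described as "including plasma lactate (detectable limit, 0.3 to 20 mmol/L) and glucose (detectable limit, 20-500 mg/dL) levels".

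Three other statements help to place those draws:

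- Anesthesia and cardiopulmonary bypass says anticoagulation was achieved "by intravenous administered heparin 300 U/kg prior to cannulation, standard hypothermic CPB" and its circuit following in sequence.
- Data collection says the clotting time "was tested by ACT Plus (Medtronic, Minneapolis, MN, USA) after heparin administration, during CPB, after protamine administration". It therefore names an on-bypass time for that test, separate from the post-heparin time, and names none for the blood gas.
- Treatment protocol says "Following standard rewarming and deaerating, the pump flow was reduced to 0.5 l/min for release of aortic clamp". This orders clamp release after rewarming but does not say when the preceding gas is drawn.

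Statistical analysis compares means of continuous variables by Student t-test, two-sided at 0.05. No baseline adjustment is described.

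**The concern.** The randomised treatment acts over one interval, rewarming. To describe what happened in that interval, one needs a value at its start. The schedule as written guarantees none. Between the post-heparin draw and the infusion lie cannulation, cooling and the hypothermic phase at 26-30 °C, over which lactate, glucose and acid-base status may shift by different amounts in different patients.

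Three things are at stake:

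1. Balance of these variables at allocation cannot be shown. This matters more because the available text describes no allocation method, concealment or blinding.
2. A change from the post-heparin or pre-incision value combines hypothermic bypass with rewarming, so it cannot be read as change during rewarming.
3. Variation that arises on bypass before allocation stays in the error term, and the existing pre-incision value cannot remove it.

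The pre-unclamping draw adds a hazard. If it is taken after the infusion starts and then used as a baseline, adjusting for it could remove part of the NTG effect.

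**Working it through.** **Event order.** Combining the sections gives: pre-incision gas; heparin; post-heparin gas; cannulation and hypothermic bypass; allocation; rewarming with infusion; clamp release; later gases. The pre-unclamping gas has no fixed place other than before clamp release. It may precede the infusion, fall early in it, or fall late in it. The last gas certain to precede NTG is therefore the post-heparin one. It reads as pre-bypass because heparin comes before cannulation and because the clotting-time schedule separates post-heparin from on-bypass.

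**Is the between-arm contrast biased?** The plan gives no figure to reproduce. A simulation (4,000 runs per setting; assumed 50 per arm, pre-bypass SD 1, bypass rise of mean 2 and SD 0.5, 1 or 2, later noise SD 1) gave the planned t-test a type I error of 4.8% to 5.2%. With a true difference of 0.8, the mean estimate was 0.79 to 0.80. There is no bias. In the same simulation, as the bypass SD rose from 0.5 to 2, power fell from 75% to 36% for the t-test and from 94% to 42% for ANCOVA on the pre-bypass value. It stayed near 97% for ANCOVA on a pre-rewarming value.

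**Precision in lactate units.** All inputs are assumed: 50 per arm, pre-incision SD 0.5, rewarming-change SD 0.6, bypass-change SD *s*, true effect 0.5 mmol/L. Independent components add, with full carry-over into later values. The formula is SE = √(2V/50), where V is:

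- unadjusted: 0.25 + s² + 0.36
- adjusted for the pre-incision value: s² + 0.36
- adjusted for a pre-infusion value: 0.36

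For s = 0.8, V is 1.25, 1.00 and 0.36, so SE = √0.0500 = 0.22, √0.0400 = 0.20 and √0.0144 = 0.12. Power is from the noncentral t, two-sided 0.05, with 98 df unadjusted and 97 adjusted.

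| Bypass SD *s* | SE unadj. / pre-incision / pre-infusion | Power unadj. / pre-incision / pre-infusion |
|---|---|---|
| 0.2 | 0.16 / 0.13 / 0.12 | 87% / 97.5% / 98.5% |
| 0.5 | 0.19 / 0.16 / 0.12 | 76% / 89% / 98.5% |
| 0.8 | 0.22 / 0.20 / 0.12 | 60% / 70% / 98.5% |
| 1.2 | 0.29 / 0.27 / 0.12 | 41% / 45% / 98.5% |

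Relative to using the existing pre-incision value, the gain is 98.5 − 97.5 = 1 point at s = 0.2 and 98.5 − 45 = 53.5 points at s = 1.2.

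**Sensitivity to carry-over.** If only half of the value at rewarming carries into later values, the pre-incision adjustment has V = 0.25s² + 0.36. Power is then 97%, 93% and 83% at s = 0.5, 0.8 and 1.2, against 98.5%. The gains are about 2, 6 and 15 points.

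**Unseen chance imbalance.** The SE of the arm difference in the bypass component alone is s√(2/50) = 0.2s, which is 0.10, 0.16 and 0.24 mmol/L at s = 0.5, 0.8 and 1.2.

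**The case against.** A reader might infer that bypass changes are confounded with the NTG effect and that the two cannot be separated. The documents do not support that. Allocation is random and follows those changes, so they are balanced in expectation and the difference between arms in later samples still estimates the NTG effect. Inability to separate them applies only to within-patient or within-arm change from a pre-bypass sample.

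A reader might also infer that the pre-unclamping gas is always taken after rewarming. Treatment protocol places clamp release there, not the draw. If that draw in fact preceded the infusion, it would already be the missing baseline, and the defect would be only an unstated time.

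Further, the list is introduced as inclusive, and Anesthesia and cardiopulmonary bypass mentions serial gases for ventilation, so an on-bypass gas may exist in practice. This stands as a caution, but no such draw is specified, so none is guaranteed for every patient.

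The importance of these variables is also uncertain. The available text names no primary endpoint, and lactate and glucose sit beside inotropic use, extubation time, length of stay and 30-day mortality.

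Finally, the power gain rests wholly on assumed inputs and comes only through an adjusted analysis. An extra sample fed into the planned t-test on raw values would gain nothing. Part of the loss is already recoverable from the pre-incision value (76% to 89% at s = 0.5). All of this stands and limits the size of the point. None of it supplies a pre-infusion value.

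**Conclusion.** The point holds as one of precision, balance checking and interpretation, not of bias. As written, the schedule guarantees no blood gas between the start of bypass and the start of the infusion, and it leaves the pre-unclamping draw undefined relative to treatment. Consequently, balance at allocation cannot be checked or adjusted for, and change from the available baselines cannot be attributed to rewarming.

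The loss of precision is of unknown size. It is negligible if little happens to these variables before rewarming or if little carries forward, and large if patients vary widely on bypass. The range of about 1 to over 50 points depends on the assumed arm size, SDs, effect and carry-over, none of which the documents give. The change is worth making because it is cheap, not because the comparison is invalid without it.

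**What to change.** **Data collection.** Add one blood gas with lactate and glucose, taken from the existing arterial line on bypass immediately before the study infusion starts. Record the time of every draw, including the pre-unclamping one, relative to infusion start.

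**Statistical analysis.** Compare post-infusion lactate, glucose and acid-base values by ANCOVA with the pre-infusion value as covariate, in place of the unadjusted t-test. State that no draw taken after infusion start will serve as a baseline.

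**Cost.** One extra point-of-care run per patient, time stamps, and a little more analysis. No treatment changes.

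**If sampling is already complete.** Report draw times relative to infusion, adjust for the last value known to precede it, and do not attribute change from pre-bypass samples to rewarming.
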